### 3.2. Brief Description

This Phase 2, multicenter, randomized, double-blind, placebo-controlled, parallel-group study with a 2-week single-blind Run-in Period will evaluate the safety and pharmacodynamics (PD) of oral olinciguat compared with placebo when administered QD for approximately 12 weeks in participants with SCD.

At the Screening Visit, participants will undergo preliminary procedures to determine their initial eligibility. At the Run-in Visit (which will occur at least 3 calendar days after the Screening Visit), eligible participants will then begin 14 to 17 days of single-blind placebo dosing and will begin recording their daily and weekly symptom assessments in an electronic diary (eDiary).

On Day 1 of the Treatment Period, participants who continue to be eligible will be randomized to double-blind study drug (QD olinciguat or placebo). Note that participants enrolled under protocol Amendment 3 or earlier were randomized differently than those randomized under Amendment 4 and later, as described below.

- Under Amendment 3 or earlier: Participants were randomly assigned in a 1:1:1:1 ratio to placebo, 2 mg olinciguat, 4 mg olinciguat, or 6 mg olinciguat (see [Table 3](#))
- Under Amendment 4 and later: Participants were randomly assigned in a 3:1 ratio to 18 mg olinciguat or placebo (see [Table 4](#))

On Day 1 and for each up-titration visit, participants must remain in the clinic at least 6 hours postdose and will be allowed to leave thereafter at the Investigator's discretion.

At all scheduled study visits, participants will undergo safety, efficacy, and PK assessments and, as applicable, will take the relevant study drug dose and will be issued study drug supply for subsequent at-home QD dosing. In addition, participants will receive scheduled phone calls in between the scheduled visits to monitor TEAEs and concomitant medications and procedures. Throughout the Treatment Period, participants will continue completing the patient-reported outcome (PRO) questionnaires each day in their eDiary.

Beginning in March 2020, remote visits via phone call have been allowed to accommodate the impact of COVID-19 on study visits and participants' safety. The phone visits, when necessary, have been utilized to collect adverse event, concomitant medication, select vital sign timepoints, uptritration eligibility, and other relevant data.

As much as possible, participants will return to the clinic about 28 days after their last study drug dose for final Follow-up assessments.

### 3.3. Participant Selection

The study will select participants with SCD according to the inclusion/exclusion criteria listed in the relevant version of the protocol.

### 3.4. Determination of Sample Size

For this Phase 2 study, an overall sample size of approximately 88 participants is planned. Of these participants, approximately 40 are expected to be randomized under Protocol Amendment 3 or earlier and approximately 48 participants are expected to be randomized under Amendment 4 and later (see [Section 3.5](#)). The sample size was determined outside of statistical considerations and is considered reasonable based on precedent set by prior studies of similar nature and design.

This document is confidential.

### 3.5. Treatment Assignment

During the Run-in Period, all participants will receive placebo in a single-blind manner (Table 2).

Table 2. Dose Regimen During Single-blind Run-in Period

Dosage	Run-in (Day -17 or -14 to Day -1); QD Dose
placebo daily	1×matching placebo tablet
QD=once daily	

The Treatment Period is double blind and placebo controlled. Participants will be randomized through central randomization based on the protocol applicable at the time. The computer-generated randomization schedule will be prepared by an independent statistician not otherwise associated with the conduct of the study.

Under Protocol Amendment 3 or earlier, eligible participants will be stratified by hydroxyurea (HU) use and randomly assigned in a 1:1:1:1 ratio to 6 mg olinciguat, 4 mg olinciguat, 2 mg olinciguat, or placebo at Randomization Visit on Day 1 (Table 3).

Table 3. Dose Regimen by Treatment Period Week for Participants Randomized Under Amendment 3 and Earlier

Randomized Dose Level	Week 1=half dose		Weeks 2 to 12=full dose *	
	Dosage	QD Dose	Dosage	QD Dose
6 mg IW-1701	3 mg IW-1701 daily	1 × 3-mg IW-1701 tablet	6 mg IW-1701 daily	2 × 3-mg IW-1701 tablet
4 mg IW-1701	2 mg IW-1701 daily	1 × 2-mg IW-1701 tablet	4 mg IW-1701 daily	2 × 2-mg IW-1701 tablet
2 mg IW-1701	1 mg IW-1701 daily	1 × 1-mg IW-1701 tablet	2 mg IW-1701 daily	2 × 1-mg IW-1701 tablet
Placebo	Placebo daily	1 × matching placebo tablet	placebo daily	2 × matching placebo tablet

Under Amendment 4 and later, eligible participants will be stratified by HU use and randomly assigned in a 3:1 ratio to 18 mg olinciguat or placebo (Table 4).

Table 4. Dose Regimen by Treatment Period Week for Participants Randomized Under Amendment 4 and Later

Initial Dose Level (Day 1-Day 7)		Week 1 through Week 3 (Day 8-Day 28)		Week 4 through Week 12 (Day 29-Day 85)	
QD Dose	QD Dosage	QD Dose	QD Dosage	QD Dose	QD Dosage
6 mg IW-1701 daily	2×3-mg IW-1701 tablet	12 mg IW-1701 daily	4×3-mg IW-1701 tablet	18 mg IW-1701 daily	6×3-mg IW-1701 tablet
PBO daily	2×matching PBO tablet	PBO daily	4×matching PBO tablet	PBO daily	6×matching PBO tablet

### 3.6. Blinding and Unblinding

Unblinding of a participant's randomized treatment assignment to the Investigator or Sponsor personnel

This document is confidential.

involved in study conduct is restricted to emergency situations in which knowledge of the treatment is necessary for the proper handling of the participant. Except in a medical emergency, the Investigator and study center staff will remain blinded during the conduct of the study and until, at a minimum, all discrepancies in the clinical database are resolved (ie, at the time of the database lock).

The Sponsor may also break the blind if necessary for mandatory Regulatory Reporting to the Health Authorities.

To allow for ongoing safety monitoring during the study, members of an external Data Monitoring Committee (DMC) as well as the Sponsor's Pharmacovigilance group will review summaries of adverse event (AE) data and may request unblinded safety data.

### **3.7. Administration of Study Medication**

Throughout the Run-in and the Treatment Period, participants will be instructed to take study drug QD with water, in the morning, at approximately the same time each day, at least 1 hour before or 2 hours after food. [Table 2](#), [Table 3](#), and [Table 4](#), respectively, summarize the dosing regimens during the Run-in Period (all protocol versions), the Treatment Period under Amendment 3 and earlier, and the Treatment Period under Amendment 4 and later.

On study visit days, study drug will be administered in the clinic after predose assessments to allow measurements at trough plasma levels. Study visits should be scheduled in the morning to accommodate participants' regular dosing schedules and fasting requirements.

### **3.8. Study Procedures and Flowchart**

The study schedule from screening through follow-up under Protocol Amendment 3 is presented in [Table 5a](#). (See respective study protocol for minor differences in the Schedule of Events for the original protocol through Amendment 2.) The study schedule under Protocol Amendments 4/5 is show in [Table 5b](#).

This document is confidential.

Table 5a Schedule of Events (Amendment 3)

Study Period →	Screening	Run-in	Treatment										F/U
Contact Type →	Visit	Visit	Visit	Call	Visit	Calls	Visit	Call	Visit	Call	Visit	Visit	Visit
Visit Name →	Screening	Run-in*	Randomization	-	Week 1	-	Week 4	-	Week 8	-	Week 12/ EOT		F/U
Day (D) → Procedure ↓	Day -43 to -15	Day -17 to -14	Day 1	Day 2	Day 8 ±1	Wk1 V+1D, D15±1, D22±1	Day 29 ±3	D43 ±1	Day 57 ±7	D71 ±1	Day 85 -7/+4	Day 113 -3/+7	
ICF signed	X												
I/E confirmation	X	predose	predose										
Demographics	X												
Medical history	X												
Prior & concomitant meds & procedures	X	X	X	X	X	X	X	X	X	X	X	X	
Physical exam (a)	X	predose	predose		predose		predose		predose		predose		X
Weight & height	W, H	W	W		W		W		W		W		W
12-lead ECG (b)	X		predose pd: 4h (±15m)		predose pd: 4h (±15m)								X
AE evaluation	X	X	X	X	X	X	X	X	X	X	X	X	
Drug screen (c)	X												
Pregnancy test (d)	X	predose	predose		predose		predose		predose		predose		X
Urinalysis sample	X		predose		predose		predose		predose		predose		X
Oral temperature and RR	X		predose pd: 1h (±15m)		predose		predose		predose		predose		X
O 2 saturation	X	predose	predose		predose		predose		predose		predose		X
Seated BP, pulse (e)	X		pd: 6h (±15m)		predose pd: 6h (±15m)								
Seated-to-standing BP/pulse (f)	X	X	predose pd: 1,3,6 (±15m)		predose pd: 1,3,6 (±15m)		predose pd: 1h (±15m)		predose pd: 1h (±15m)		predose pd: 1h (±15m)		X

This document is confidential.

Study Period →	Screening	Run-in	Treatment										F/U
Contact Type →	Visit	Visit	Visit	Call	Visit	Calls	Visit	Call	Visit	Call	Visit	Visit	Visit
Visit Name →	Screening	Run-in*	Randomization	-	Week 1	-	Week 4	-	Week 8	-	Week 12/ EOT	F/U	
Day (D) Procedure ↓	Day -43 to -15	Day -17 to -14	Day 1	Day 2	Day 8 ±1	Wk1 V+1D, D15±1, D22±1	Day 29 ±3	D43 ±1	Day 57 ±7	D71 ±1	Day 85 -7/+4	Day 113 -3/+7	
Clinical laboratory blood samples	X		predose		predose		predose		predose		predose	X	
Genotyping blood sample (w/consent)			predose										
PK blood sample			predose pd: 1,2,4,5h (±15m)		predose pd: 1,2,4,5h (±15m)		predose pd: 2h (±1h)		predose pd: 2h (±1h)		predose pd: 2h (±1h)	X	
Blood samples for biomarkers			predose pd: 5h (±15m)		predose						predose	X	
Blood samples for platelet biomarkers			predose pd: 5h (±15m)				predose				predose		
eDiary registration /training		predose											
eDiary device check			predose										
PROMIS Fatigue; Absences		predose	predose		pd: ≤1h		pd: ≤1h		pd: ≤1h		pd: ≤1h		
ASCQ-Me		predose			pd: ≤1h		pd: ≤1h		pd: ≤1h		pd: ≤1h		
PGIC											pd: ≤1h		
EQ-5D-5L & SF-12v2		predose	predose								pd: ≤1h	X	
Randomization			X										
Study drug supply	X	X					X		X				
In-clinic study drug dosing (g)	X	X			X		X		X		X		
Study drug return & MEMScap review			X		X (h)		X		X		X		
eDiary return											X		
Transfer: Cognitive debrief, patient contact info (i)											X		
Study completion												X	

This document is confidential.

AE=adverse event; ASCQ-Me=Adult Sickle Cell Quality of Life Measurement Information System; BP=blood pressure; debrief.=debriefing; D=Day(s); ECG=electrocardiogram; EOT=end of treatment; EQ-5D-5L=EuroQOL 5-dimension questionnaire; F/U=follow-up; h=hour(s); H=height; ICF=informed consent form; I/E=inclusion/exclusion; m=minute(s); MEMS=Medication Event Monitoring System; O2=oxygen; pd=postdose; PGIC=Patient Global Impression of Change; PK=pharmacokinetic(s); pre=predose; PROMIS=Patient-reported Outcomes Measurement Information System; RR=respiratory rate; SF12v2=Short Form Health Survey Version 2; temp=temperatures; V=Visit; W=weight; Wk=Week

\* The Run-in Visit must occur at least 3 calendar days after the Screening Visit.

- a. For Treatment Period visits, physical exam may be symptom directed but must include the cardiovascular and respiratory systems.
- b. Patient must be supine for  $\geq 5$  m before the ECG recording. If QTc result is outside of normal range, perform in triplicate and calculate the average. If ECG result is clinically abnormal, repeat. If repeated ECG is also clinically abnormal, site should follow standard institutional procedures until resolved. If concerns remain, issue should be escalated to Medical Monitor.
- c. Urine screen for amphetamines, barbiturates, benzodiazepines, cocaine, opiates, phencyclidine, and propoxyphene.
- d. For female patients, a negative pregnancy test by urine dipstick must be documented at all study visits; negative results must be confirmed before each in-clinic dosing. If urine test is positive, see Section 3.8.7.2. All patients should be reminded of birth control requirements
- e. Seated BP at the Screening Visit, 6 hours postdose at the Randomization Visit, and predose and 6 hours postdose at the Week 1 Visit will be the average of 3 measurements obtained at 2-m intervals after patient has been sitting quietly for  $\geq 5$  m. Other BP and all pulse measurements will be single measurements obtained after the patient has been sitting quietly for  $\geq 5$  m.
- f. Patient must sit quietly for approximately  $\geq 5$  m before seated BP and pulse measurements are taken, and then assume standing position for 2 m ( $\pm 1$  m) before standing BP and pulse measurements are taken. Vital signs (including BP) must be measured before blood sampling, when applicable.
- g. Study drug will be administered in the clinic on study visit days after predose assessments. Patients should take study drug 1 hour before or 2 hours after food, with water, and may swallow 2 tablets together, when applicable. Study drug may be taken with concomitant medications. Coffee or juice may be allowed if the patient feels faint.
- h. At the Week 1 Visit, patients will bring the study drug bottles dispensed on Day 1 to the clinic. MEMScaps will be read and the patient will receive their Day 8 ( $\pm 1$ ) study drug dose in the clinic from the Day 1 bottles. The subject will continue to dose from the Day 1 bottles until they return for the Week 4 Visit. Patients who qualify will begin taking the up-titrated dose; see Section 3.5.4.2 for up-titration requirements.
- i. *For patients participating in the cognitive debriefing interview study:* Prior to EOT Visit (including early terminations  $\geq 4$  weeks post randomization), study staff will transfer the patient's contact information (name, subject ID, phone number, email address) and EOT visit date to Adelphi Values with notification that the patient has scheduled their EOT Visit. See Section 3.8.9.4.

This document is confidential.

Table 5b. Schedule of Events (Amendments 4 and 5)

Study Period	Screening				Treatment						F/U		
Contact Type	Visit	Visit	Visit	Call	Visit	Calls	Visit	Calls	Visit	Call	Visit	Visit	
Visit Name	Screening	Run-in a	Randomization	-	Week 1	-	Week 4	-	Week 8	-	Week 12/EOT	F/U/ EOS	
Day (D) → Procedure 	Day -43 to -15	Day -17 to -14	Day 1	Day 2	Day 8 ±1	Wk1 V+1D, D15±2, D22±2	Day 29 ±3	Wk4 V+1D ±2	D43 ±2	Day 57 ±7	D71 ±2	Day 85 -7/+4	Day 113 -3/+7
ICF signed	X												
I/E confirmation	X	predose	predose										
Demographics	X												
Medical/SCD history	X												
Prior & concomitant meds & procedures	X	X	X	X	X	X	X	X	X	X	X	X	
Physical exam b	X	predose	predose		predose		predose		predose		predose		X
Weight & height	W, H	W	W		W		W		W		W	W	
12-lead ECG c	X		predose pd: 4h (=15m)		predose pd: 4h (=15m)							X	
AE evaluation	X	X	X	X	X	X	X	X	X	X	X	X	
Drug screen d	X												
Pregnancy test e	X	predose	predose		predose		predose		predose		predose	X	
Urinalysis sample	X		predose		predose		predose		predose		predose	X	
Oral temperature & RR	X		predose pd:1h (=15m)		predose		predose		predose		predose	X	
O 2 saturation	X	predose	predose		predose		predose		predose		predose	X	
Seated BP, pulse f	X		pd: 6h (=15m)		predose pd: 6h (=15m)								
Seated-to-standing BP/pulse g	X	X	predose pd: 1,3,6 (=15m)		predose pd:1,3,6 (=15m)		predose pd:1h (=15m)		predose pd:1h (=15m)		predose pd:1h (=15m)	X	

This document is confidential.

Study Period		Screening		Treatment								F/U	
Contact Type	Visit	Visit	Visit	Call	Visit	Calls	Visit	Calls		Visit	Call	Visit	Visit
Visit Name	Screening	Run-in a	Randomization	-	Week 1	-	Week 4	-	-	Week 8	-	Week 12/EOT	F/U/ EOS
Day (D) → Procedure ↓	Day -43 to -15	Day -17 to -14	Day 1	Day 2	Day 8 ±1	Wk1 V+1D, D15±2, D22±2	Day 29 ±3	Wk4 V+1D	D43 ±2	Day 57 ±7	D71 ±2	Day 85 -7/+4	Day 113 -3/+7
Clinical laboratory blood samples	X		predose		predose		predose			predose		predose	X
Genotyping blood sample (w/patient consent)			predose										
PK blood sample			predose pd: EOV		predose pd: EOV		predose pd: EOV			predose pd: EOV		predose pd: EOV	X
Urine samples for UACR		predose	predose				predose					predose	X
Blood sample for biomarkers			predose		predose		predose					predose	X
Blood samples for platelet biomarkers b			predose pd: 5h(±15m)				predose					predose	
eDiary registration /training		predose											
eDiary device check			predose										
PROMIS Fatigue; Absences		predose	predose		pd: ≤1h		pd: ≤1h			pd: ≤1h		pd: ≤1h	
ASCOQ-Me		predose			pd: ≤1h		pd: ≤1h			pd: ≤1h		pd: ≤1h	
PGIC												pd: ≤1h	
EQ-5D-5L & SF-12v2		predose	predose									pd: ≤1h	X
Randomization			X										
Study drug supply/return i		X	X		X		X			X		Return only	
In-clinic study drug dosing j		X	X		X		X			X		X	
eDiary return												X	
Transfer: Cognitive debrief, patient contact info k												X	

This document is confidential.

Study Period		Screening		Treatment								F/U	
Contact Type	Visit	Visit	Visit	Call	Visit	Calls	Visit	Calls		Visit	Call	Visit	Visit
Visit Name	Screening	Run-in a	Randomization	-	Week 1	-	Week 4	-	-	Week 8	-	Week 12/EOT	F/U/ EOS
Day (D)→ Procedure ↓	Day -43 to -15	Day -17 to -14	Day 1	Day 2	Day 8 ±1	Wk1 V+1D, D15±2, D22±2	Day 29 ±3	Wk4 V+1D	D43 ±2	Day 57 ±7	D71 ±2	Day 85 -7/+4	Day 113 -3/+7
Study completion													X

AE=adverse event; ASCQ-Me=Adult Sickle Cell Quality of Life Measurement Information System; BP=blood pressure; debrief=debriefing; D=Day(s); ECG=electrocardiogram; eDiary=electronic diary; EOS=end of study; EOT=end of treatment; EOF=end of visit; EQ-5D-5L=EuroQOL 5-dimension questionnaire; F/U=follow-up; h=hour(s); H=height; ICF=informed consent form; I/E=inclusion/exclusion; m=minute(s); O2=oxygen; pd=postdose; PGIC=Patient Global Impression of Change; PK=pharmacokinetic(s); pre=predose; PROMIS=Patient-reported Outcomes Measurement Information System; RR=respiratory rate; SF12v2=Short Form Health Survey Version 2; temp=temperatures; UACR=urine albumin-to-creatinine ratio; V=Visit; W=weight; Wk=Week

- The Run-in Visit must occur at least 3 calendar days after the Screening Visit. The Run-in dosing period will continue for 14 to 17 days; see Section 3.1.
- For Treatment Period visits, physical exam may be symptom directed but must include the cardiovascular and respiratory systems.
- Patient must be supine for ≥5 m before the ECG recording. If QTc result is outside of normal range, perform in triplicate and calculate the average. If ECG result is clinically abnormal, repeat. If repeated ECG is also clinically abnormal, site should follow standard institutional procedures until resolved. If concerns remain, issue should be escalated to Medical Monitor.
- Urine screen for amphetamines, barbiturates, benzodiazepines, cocaine, opiates, phencyclidine, and propoxyphene.
- For women of reproductive potential, a negative pregnancy test by urine dipstick must be documented at all study visits; negative results must be confirmed before each in-clinic dosing. If urine test is positive, see Section 3.8.7.2. All patients should be reminded of birth control requirements.
- Seated BP at the Screening Visit, 6 hours postdose at the Randomization Visit, and at predose and 6 hours postdose at the Week 1 Visit will be the average of 3 measurements obtained at 2-m intervals after patient has been sitting quietly for ≥5 m. Other BP and all pulse measurements may be single measurements obtained after the patient has been sitting quietly for ≥5 m.
- Orthostatic measurements:* Patient must sit quietly for approximately ≥5 m before seated BP and pulse measurements are taken, and then assume standing position for 2 m (±1 m) before standing BP and pulse measurements are taken. Vital signs (including BP) must be measured before blood sampling when applicable.
- Not collected at sites located in Lebanon
- Starting with the Run-in Visit and throughout the Treatment Period, patients will be instructed to bring all study drug bottles to each clinic visit for confirmation of at-home dosing compliance via tablet count. Study drug will be resupplied as applicable.
- Study drug will be administered in the clinic on study visit days after predose assessments. Patients should take study drug 1 hour before or 2 hours after food, with water, and may swallow 2 tablets together, when applicable. Study drug may be taken with concomitant medications. Coffee or juice may be allowed if the patient feels faint. During the Treatment Period, dose levels will be titrated as indicated in Table 2 for patients meeting criteria in Section 3.5.4.2. See Section 3.5.4.3 for dose adjustment instructions. Instructions for temporary dosing interruptions are in Section 3.5.4.4.
- For patients participating in the cognitive debriefing interview study:* Prior to EOT Visit (including early terminations ≥4 weeks post randomization), study staff will transfer the patient's contact information (name, subject ID, phone number, email address) and EOT visit date to Adelphi Values with notification that the patient has scheduled their EOT Visit. See Section 3.8.9.4.

This document is confidential.

## **4. Analysis Populations**

The following analysis populations are defined for this study. The different analysis populations will be listed.

### **4.1. Screened Population**

The Screened Population will include all participants who sign the informed consent form and receive a participant identification number.

### **4.2. Single-blind Run-in Population**

The Single-blind Run-in Population will include all participants who enter the single-blind Run-in period and receive 1 dose of single-blind study drug (placebo).

### **4.3. Safety Population**

The Safety Population will include all randomized participants who receive at least 1 dose of double-blind study drug. Participants in this population will be evaluated according to the treatment they actually received.

### **4.4. Intent-to-Treat Population**

The Intent-to-Treat (ITT) Population will include all randomized participants. Participants in this population will be evaluated according to the treatment arm they were assigned at randomization.

### **4.5. Pharmacokinetic Population**

The PK Population will include all randomized participants who receive at least 1 dose of olinciguat and have at least 1 evaluable postdose PK concentration assessment.

### **4.6. Evaluable Population**

The Evaluable Population will include all randomized participants with no major protocol deviations (Section 4.7) who complete at least 6 weeks of double-blind study drug. Participants with unexpected plasma concentration values will be excluded (ie, participant who were randomized to placebo but have consistently measurable plasma concentrations of olinciguat and participants randomized to olinciguat with consistent BLQ concentration values). These participants will be identified by the pharmacokineticist at Cycleron before database lock and unblinding.

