5.3 ANALYSIS POPULATIONS

The following populations will be defined for this study:

- **Screened Population:** All patients who sign the informed consent form and receive a patient identification number
- **Single-blind Run-in Population:** All patients who enter the single-blind Run-in period
- **Safety Population:** All randomized patients who receive at least 1 dose of study drug. Patients in this population will be evaluated according to the treatment they actually received.
- **Intent-to-Treat (ITT) Population:** All randomized patients. Patients in this population will be evaluated according to the treatment arm they were assigned to at randomization
- **PK Population:** All randomized patients who receive at least 1 dose of IW-1701 and have at least 1 evaluable postdose PK parameter assessment
- **Evaluable Population:** All randomized patients with no major protocol deviations who complete at least 8 weeks of treatment (a blinded data review will determine if a more stringent criterion, eg, 10 weeks, is appropriate)

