### **4.7. Protocol Deviations**

Protocol deviations and major protocol deviations will be identified and documented based on a review of protocol deviations before database lock and treatment unblinding and will be used to define the Evaluable Population. The categories of major protocol deviations to be reviewed include, but are not limited to, participants who:

- Did not meet key inclusion/exclusion criteria in the judgement of the evaluability committee.
- Received disallowed concomitant medication that could meaningfully impact results.
- Had overall treatment compliance rate <80% or >120% (including Single-blind Run-in Period and Double-blind Treatment Period).

This document is confidential.

In addition, the sub-categories 'Related to COVID-19' and 'Unrelated to COVID-19' will be collected to assess the impact of COVID-19 on the protocol deviation data.

The number and percentage of participants with major protocol deviations will be summarized by type of deviation and relationship to COVID-19 and by treatment arm for the ITT Population. All protocol deviations will be presented in a data listing.

This document is confidential.

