## 8. Pharmacodynamic (PD) Analyses

All PD analyses except the PRO analyses will be based on the Safety and Evaluable Populations. PRO analyses will be based on the ITT and Evaluable Populations. Listings will be provided for all PD-related data.

For the treatment comparisons by statistical modeling:

- comparisons between 18 mg olinciguat group vs. the matched placebo group (PBO2) enrolled under Protocol Amendments 4 and later
- comparisons between each olinciguat group (2 mg, 4 mg, 6 mg, and 18 mg) vs. the overall placebo group combined from all protocols

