### 8.2. Vaso-occlusive Crisis (VOC)

#### 8.2.1. Primary Analysis of Exploratory VOC Parameters

Sickle cell-related pain crisis events will be documented as 'vaso-occlusive crises' (VOCs) on the AE eCRF page throughout the duration of the trial and adjudicated by an independent adjudicator. Only

This document is confidential.

adjudicated events that are deemed VOCs will be utilized in the endpoints defined below. An on-study sickle cell-related VOC is defined in [Section 5.2.5](#).

Acute chest syndrome, hepatic sequestration, splenic sequestration, priapism (each requiring a visit to a medical facility or documented telephone management) and death (except that due to suicide, accident, or other event clearly unrelated to the participant's medical condition) will also be considered VOCs, as well as subtypes of VOCs, for analysis purposes.

The exploratory VOC parameters are listed here:

- Time to first VOCs experienced during the Treatment Period, defined as (start date of VOC – the date of first dose of double-blind study drug + 1)
- Proportion of participants experiencing  $\geq 1$  VOC during the Treatment Period
- Annualized VOC rate during the Treatment Period, defined as  $365^*$  total number of events/ (last dose date – first dose date of double-blind study drug +1)

All 3 VOC parameters will be summarized by descriptive statistics by treatment group.

The time to first VOC will be summarized using Kaplan Meier method; the median event time (if appropriate) and 2-sided 95% CI for the median will be provided; 25% and 75% percentiles will also be presented. Additionally, the Kaplan Meier plots will be generated. For comparison between each olinciguat group and the corresponding placebo group, P-value will be generated from log-rank test.

Example SAS code for Kaplan Meier method is shown below:

```
Proc lifetest data=analysis_data;
  Time AVAL*CNSR(1);
  Strata trt;
Run;
```

For the proportion of participants experiencing  $\geq 1$  VOC (dichotomous endpoint), the proportions for each olinciguat treatment group and the corresponding placebo group will be compared using a Cochran-Mantel-Haenszel (CMH) test controlling for stratification factors (HU use). The difference in the proportions between each olinciguat group and the placebo group as well as the CMH estimates of odds ratio, risk difference, and p-values will be presented, along with the corresponding 2-sided 95% CIs.

Example SAS code for CMH model is listed as below:

```

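### VOC endpoints counted from Day 1 are also tested in the Evaluable Population, whose 6-week drug requirement an early crisis or death can itself make a participant fail

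*SAP*

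**What the plan says.** SAP Section 8 sets the populations for the whole chapter: "All PD analyses except the PRO analyses will be based on the Safety and Evaluable Populations". VOC is Section 8.2 of that chapter. No exception is made for it, and neither population is named as leading.

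SAP 8.2.1 defines three VOC endpoints. "Time to first VOCs experienced during the Treatment Period" is measured from "the date of first dose of double-blind study drug". The proportion with at least one VOC and the "Annualized VOC rate during the Treatment Period" cover the same period, and the rate is divided by the participant's own days from first to last dose. The section also counts as a VOC any "death (except that due to suicide, accident, or other event clearly unrelated to the" participant's condition). Treatment groups are compared by log-rank, CMH and stratified Wilcoxon tests.

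SAP 4.6 admits to the Evaluable Population only participants with no major protocol deviation "who complete at least 6 weeks of double-blind study drug". The deviation categories to be reviewed under SAP 4.7 include overall compliance below 80% or above 120%, and "Received disallowed concomitant medication that could meaningfully impact results". Protocol 5.3 has the same structure with a longer requirement, "who complete at least 8 weeks of treatment".

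SAP 8.2.2 runs the sensitivity analysis of the VOC rate in the Safety Population only.

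**The concern.** Events are counted from Day 1, but whether a participant belongs to the Evaluable Population is settled later, by a condition that the event can cause them to fail. A participant whose early crisis or death ends treatment is removed together with that event. No landmark start is set, and there is no exception for stopping because of a VOC. The choice between 6 and 8 weeks does not matter here: any minimum-exposure rule combined with events counted from Day 1 has this property.

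At stake is the Evaluable set of Kaplan-Meier curves, tests and rates. These come with p-values, stand beside the Safety results with equal standing, and could be read as the effect in participants who took the drug as planned.

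**Working it through.** The documents give no event rate, effect size or power for the VOC endpoints, so there is no figure of the plan's own to reproduce. The structure can be checked directly. The size can only be illustrated.

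**Window.** Six weeks is 42 days and the Treatment Period runs to Day 85 (Protocol 3.1): 42/85 = 49% of the window is closed to any event that ends treatment.

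**Death.** Allocation from Amendment 4 is 3:1 of about 48 (SAP 3.4, 3.5), so about 36 on 18 mg and 12 on placebo. One VOC death before Week 6 on 18 mg is 1/36 in Safety and 0/35 in Evaluable.

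**Crisis that stops treatment.** VOCs are recorded on the adverse event page (SAP 8.2.1), and an adverse event is a listed reason for discontinuation (Protocol 3.4.2). The route is therefore open, but no frequency is given.

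**Compliance.** Assume full titration, a 14-day run-in and dosing to Day 85. Expected tablets are 14×1 + 7×2 + 21×4 + 57×6 = 14 + 14 + 84 + 342 = 454. Falling below 80% needs more than 0.20 × 454 = 90.8 missed tablets, that is 91/6 = 15.2, or 16 missed six-tablet days. Missing every dose from Day 8 to Day 28 still gives (454 − 84)/454 = 81.5%. This route is weak.

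**Illustration 1.** Assume constant hazard, equal 12-week risk p12 in both arms, and a share d of early-VOC participants who lose Evaluable status, with no other exclusions.
- p6 = 1 − √(1 − p12)
- Evaluable risk = (p12 − d·p6)/(1 − d·p6)
- With p12 = 0.40, p6 = 0.2254.
- d = 0.1: (0.40 − 0.0225)/(1 − 0.0225) = 38.6%
- d = 0.3: (0.40 − 0.0676)/(1 − 0.0676) = 35.6%
- d = 0.5: (0.40 − 0.1127)/(1 − 0.1127) = 32.4%

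With d = 0.3 on 18 mg and 0.1 on placebo, the odds ratio is 0.88 although the true risks are equal; with 0.5 and 0.1 it is 0.76. Over p12 from 30% to 50%, these two pairs give false differences of −2.4 to −7.1 points.

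**Illustration 2.** Assume a constant rate L per year, with each VOC stopping drug with probability s.
- P(at least one VOC) = 1 − exp(−85L/365)
- In Evaluable: 1 − exp(−85L/365)/exp(−42sL/365)
- With L = 3 (within the 1 to 10 crises per year allowed by inclusion criterion 6), the risk is 50.3% without the 6-week rule.
- In Evaluable it is 50.3% at s = 0, 49.4% at s = 0.05 and 45.8% at s = 0.25.

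**Opposite direction.** The 6-week rule also removes early dropouts without a VOC, which both models ignore. Assume 36 participants, 14 with a VOC; 2 stop early because of a VOC and 6 for other reasons. Safety gives 14/36 = 38.9%; Evaluable gives 12/28 = 42.9%, which is higher.

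**Annualized rate.** One VOC with the last dose on Day 10 gives 365/10 = 36.5 per year. With at least 42 days on drug, one VOC gives at most 365/42 = 8.7.

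**The case against.** The strongest reply is that nothing is lost to the study. Every VOC analysis is also run in the Safety Population, which keeps all randomized participants with at least one double-blind dose. The endpoints are exploratory and unpowered, do not appear in SAP Table 1, and outcome-dependent membership is a familiar limit of any per-protocol type of set. This stands, and it keeps the point modest. It does not remove it, because the Evaluable comparison carries p-values and is not labelled supportive. Reviewing deviations before unblinding does not help either: it hides the arm, not the crisis.

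A reader might infer that a crisis readily causes failure of every Evaluable condition. The documents do not support that. A VOC is not among the mandatory reasons for stopping drug (Protocol 3.4.2), and restart after an interruption of more than 7 days is possible (Protocol 3.5.4.4). The compliance rule is hard to fail through a short admission. The disallowed-medication rule is a matter of judgement, and nothing in the text ties the prohibited drugs to the treatment of a crisis.

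A minimum exposure also has a purpose: it limits extreme annualized rates from very short treatment. That is a fair reason for caution about the Safety rate, but it does not justify a rule that the outcome can trigger. The SAP's table index (Sections 15 to 17) is not visible in the public copy, so the exact Evaluable VOC outputs cannot be confirmed.

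**Conclusion.** The selection is real and follows from the text. A VOC death before Week 6 can never appear in the Evaluable analysis, and a crisis that leads to stopping drug before Week 6 is deleted. The Evaluable Kaplan-Meier, log-rank, CMH and rate results can be biased by this; the Safety results are not affected by it.

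Direction and size are not determined. A reader might infer that the Evaluable analysis understates crises in both arms, or that it favours 18 mg. Neither follows. If no non-fatal crisis leads to exclusion, such crises cause no distortion, and removal of early dropouts without a VOC can push the Evaluable risk up. Figures such as 35.6% versus 38.6% rest wholly on assumed loss rates and on the assumption that 18 mg loses more. With 36 and 12 participants at 40% risk, the standard error of the difference is √(0.24/36 + 0.24/12) = 0.163, about 16 points, so illustrated shifts of 2.4 to 7.1 points lie well inside chance variation.

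This is a defect in one of two parallel exploratory analyses, worth correcting because the correction is cheap.

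**What to change.** In SAP 8 and 8.2.1, state that the VOC comparisons use the Safety Population only, in line with SAP 8.2.2.

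If an on-regimen view is wanted, replace the Evaluable VOC tables with a landmark analysis at Day 43: participants still on drug at that day, counting only VOCs and time at risk from then on. Label it supportive and not a randomized comparison, since being on drug at Day 43 is itself a post-randomization state that crises can affect.

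The cost is SAP wording, plus one supportive set of tables that is either dropped or based on fewer events. The annualized rate in Safety will keep extreme values from short exposures, and the report should say so.
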